#### 3.0 STUDY DESIGN

#### 3.1 Description of the Study

This is a prospective, non-randomized, multi-center study. The site will have Institutional Review Board (IRB) or Ethics Committee (EC) review and approval prior to recruiting potential subjects. Up to 200 eligible subjects with cataracts will undergo cataract extraction in each eye during participation.

Subjects with satisfactory outcomes, or those opting not to pursue an optic exchange, will be entered into Cohort 1.

Subjects who opt for an HMIOL optic exchange in their primary eye will be entered into Cohort 2.

[figure not shown]

FIGURE 2 - COHORT DESIGNATION

All subjects enrolled in this study will be evaluated for at least 1 month following either primary cataract extraction or optic exchange, whichever is later (see Appendix A – Schedule of Assessments).

#### 3.2 STUDY POPULATION

After completing the informed consent process, subjects will be screened for participation in the study.

#### 3.2.1 INCLUSION CRITERIA

Rev.03, 7 January 2016 Confidential Page 14 of 32

**Document:** TDOC-0056124 **Version:** 1.0; CURRENT; Most-Recent; Effective

Status: Effective

CLARVISTA MEDICAL PROTOCOL CVM-00001 Rev.03

1. Must be able to understand and provide informed consent themselves or through a representative with a witness present on the IRB or EC approved Informed Consent Form (ICF)

- 2. Must be willing and able to return for scheduled treatment and follow-up examinations for at least month study duration
- 3. Must be at least 22 years of age or older at the time of consent
- 4. Planned removal of cataracts (cortical, nuclear, subcapsular, or a combination) by manual phacoemulsification cataract extraction
- 5. Dilated pupil size ≥ 6 mm in primary study eye

#### 3.2.2 EXCLUSION CRITERIA PRIOR TO SURGERY

- 1. Participation in any other drug or device clinical trial within 30 days prior to enrolling in this study and/or during study participation
- 2. History of any ocular conditions which could affect the stability of the IOL (e.g. pseudoexfoliation, zonular dialysis, evident zonular weakness or dehiscence, etc.) in either eye
- 3. Traumatic or congenital cataract
- 4. Any anterior segment pathology that may increase the risk of operative complications such as chronic iritis, uveitis, aniridia, corneal opacity, etc
- 5. Pregnancy or planned pregnancy during the study period.
- 6. Subject who, in the clinical judgment of the investigator, is not suitable for participation in the study for another clinical reason, as documented by the investigator
- 7. Taking systemic medications that, in the opinion of the investigator, may confound the outcome or increase the risk to the subject (e.g. Tamsulosin Hydrochloride Flomax) or other medications including anticholinergics, alpha adrenergic blocking agents with similar side effects (e.g. small pupil/floppy iris syndrome)

# 3.2.3 EXCLUSION CRITERIA DURING SURGERY

- 1. Vitreous loss prior to use of the investigational device
- 2. Positive posterior pressure preventing safe implantation of the lens system
- 3. Anterior chamber hyphema preventing visualization of implantation
- 4. Any zonular or capsular rupture or capsular bag instability
- 5. Intraoperative miosis preventing visualization of fixation features
- 6. Need for concomitant procedures (e.g. glaucoma surgery, LRI, RK, LASIK, etc.)

Rev.03, 7 January 2016 Confidential Page 15 of 32

**Document:** TDOC-0056124 **Version:** 1.0; CURRENT; Most-Recent; Effective

Status: Effective

CLARVISTA MEDICAL PROTOCOL CVM-00001 REV.03

7. Subject who, in the clinical judgment of the investigator, is not suitable for participation in the study for another clinical reason, as documented by the investigator

# 3.2.4 EXCLUSION CRITERIA —POST-PRIMARY CATARACT EXTRACTION (AFFECTING ELIGIBILITY FOR HMIOL OPTIC EXCHANGE)

- 1. Any clinical finding or intraocular complication during primary cataract extraction that (in the judgment of the Investigator) is likely to increase complications with optic exchange procedure or present undue risk to the subject (e.g. unexplained endothelial cell loss, post-primary cataract extraction macular edema, persistent ocular inflammation, etc.)
- 2. Presence of YAG Capsulotomy in the primary (HMIOL) eye

#### 3.3 STUDY VISITS

The timing and frequency of each assessment to be performed at each visit, will be carried out according to "Appendix A – Schedule of Assessments."

# 3.3.1 PRE-OPERATIVE VISIT - SCREENING/BASELINE (DAY -90 TO DAY 0)

After providing informed consent (see Section 4.1), prospective subjects will be screened to determine whether they meet enrollment criteria. Demographic information, relevant ocular history, and current ocular medication use will be collected. If all criteria are met, the subject will be considered enrolled, IOL calculation completed to determine appropriate HMIOL power, and the subject scheduled for surgery.

#### 3.3.2 Day 0 Visit (Primary Cataract Extraction Surgery)

Prepare the subject for surgery in the study eye and review inclusion/exclusion criteria to ensure subject still qualifies to participate.

The principal investigator will perform the cataract surgery and implant the Harmoni Modular IOL.

Once the subject is confirmed stable post-surgery, provide standard post-operative instructions and discharge.

Record any AEs, adverse device effects (ADEs), unexpected adverse device effects (UADEs), or device deficiencies (DD) (see Sections 6.1.1, 6.1.2, 6.1.3, or 6.1.4 respectively) observed pre-, intra-, or post-operatively.

In the event the subject is not implanted with an HMIOL device due to an intra-operative complication, the subject will be discontinued (see Section 4.5).

#### 3.3.3 Post-Operative Visits (Days 1-60)

All subjects implanted with a study lens will be seen for 1 Day, 1 Week, and 1 Month assessments as outlined in Appendix A.

#### 3.3.4 COHORT 2: OPTIC EXCHANGE VISIT

The Investigator will carry out the optic power determination, surgical procedure, and HMIOL optic exchange.

Rev.03, 7 January 2016 Confidential Page 16 of 32

**Document:** TDOC-0056124 **Version:** 1.0; CURRENT; Most-Recent; Effective

Status: Effective

CLARVISTA MEDICAL PROTOCOL CVM-00001 REV.03

Once the subject is confirmed stable post-surgery, provide standard post-operative instructions and discharge.

Following successful completion of HMIOL optic exchange, the subject is entered into Cohort 2. Record any AEs, ADEs, UADEs, or DDs (see Sections 6.1.1, 6.1.2, 6.1.3, or 6.1.4 respectively) observed pre-, intra-, or post-operatively.

#### 3.3.5 COHORT 2: POST-OPERATIVE VISITS (DAYS 1 - 30 POST-OPTIC EXCHANGE VISIT)

All subjects in Cohort 2 will be seen for 1 Day, 1 Week, 1 Month (post-optic exchange) assessments. (see Appendix A – Table 3).

NOTE: All concomitant medication, AE, ADE, UADE, DD, and SAE collection must be continued throughout the course of the study.

#### 3.3.6 UNSCHEDULED VISITS

If at any time during the study, outside of the above scheduled visits, the subject requests or the Investigator determines the subject should be assessed, an unscheduled visit may occur. Adverse events and concomitant medications will be recorded and assessments deemed necessary by the Investigator should be performed on either or both eyes. NOTE: Only data relevant to the primary study eye (if applicable) will be captured on the Unscheduled Visit CRFs.

If a subject is seen for multiple visits during a given visit window, the data from a visit that is intended to meet the protocol requirements for the scheduled visit should be captured in the visit CRF. Where such a determination cannot be made, the first visit within the scheduled visit window will be used for completion of the protocol required visit. If assessments are missing from that visit, however captured at subsequent visits within window, those assessments can be collected as part of the protocol visit. In such a circumstance, the visit date will remain consistent with the first visit established within the visit window, per the scenario above. Any additional and applicable data captured and associated with the Study Eye will be captured as an Unscheduled Visit.

#### 3.3.7 MISSED VISITS

If a subject misses any scheduled visit and cannot be seen prior to the start of the next visit window, the visit will be considered "missed."

#### 4.0 STUDY METHODS

Prior to recruitment of any subjects into the study, review and written approval of the protocol and informed consent must be obtained from the Institutional Review Board (IRB) or Ethics Committee (EC) by each participating clinical site.

#### 4.1 INFORMED CONSENT

Informed consent must be obtained and documented in writing prior to the initiation of any study procedures. The subject (or the subject's legally authorized representative) must be allowed sufficient time to thoroughly read (or have explained), the informed consent form. The Investigator or his/her designee should answer any questions that the subject/representative might have. If the subject agrees to participate in the study, (i.e. provides informed consent)

Rev.03, 7 January 2016 Confidential Page 17 of 32

**Document:** TDOC-0056124 **Version:** 1.0; CURRENT; Most-Recent; Effective

Status: Effective

CLARVISTA MEDICAL PROTOCOL CVM-00001 Rev.03

the subject/representative must sign two copies of the informed consent form. The witness and the Investigator must also sign both copies of the informed consent form. One copy of the informed consent form should be given to the subject/representative. If applicable, it will be provided in a certified translation of the local language. As part of the consenting process, the subjects will be informed of their right to treatment for any injuries related to the study. Any and all such treatment if necessary, will be paid for by the Sponsor to the extent it is not covered by a subject's healthcare coverage (subject to local ethics committee approval). Completion of the consenting process as well as the date of the subject's signature on the informed consent form should be noted in the subject's medical chart.

Subjects who complete the informed consent process will be screened for eligibility. Screened subjects will be recorded on site-specific screening logs and once they are determined as being eligible, they will be enrolled into the study and an HMIOL order placed with the Sponsor if necessary.

Subjects scheduled for an optic exchange will complete an addition IRB / EC approved informed consent process for this procedure.

#### 4.2 Assignment of Subject Identification

A unique and sequential subject identification number (ID) will be assigned at screening and never duplicated for another subject. This ID will be used on all study-related documents. To maintain confidentiality, the subject's name will not be recorded on any study document other than the informed consent form.

#### 4.3 SCREEN FAILURE

A record of screen failures and the reasons for the screen failures will be recorded in the subject source documents and captured in the CRF for summary.

#### 4.4 SUBJECT COMPLETION

The subject has completed the entire study when the HMIOL has been implanted and / or the Optic Exchange completed and the Sponsor receives completed electronic Case Report Form (CRF) documentation for all visits and a Study Exit CRF. Subjects who require further follow-up for an AE will be followed according to Section 6.3.4.

A Study Exit CRF must be completed for all subjects who complete the clinical investigation.

#### 4.5 Subject Discontinuation

A subject MUST be discontinued prior to the final study visit for any of the following reasons:

- Death
- Subject is enrolled and scheduled for surgery but is not implanted with an HMIOL at Day 0 (Operative Visit –
  Primary Cataract Extraction)
- Surgical complication(s) unrelated to the investigational device preventing the implantation of the HMIOL (i.e. capsulorhexis tear, zonular rupture, evident zonular weakness or dehiscence, posterior capsular rupture, vitreous loss, posterior capsular plaque, significant detached Descemet's membrane, significant anterior chamber bleeding, iris incarceration or damage, corneal endothelial touch, unsuccessful/incomplete phacoemulsification, haptic and/or optic damage/haptic amputation)
- Explantation of the HMIOL System

Rev.03, 7 January 2016 Confidential Page 18 of 32

**Document:** TDOC-0056124 **Version:** 1.0; CURRENT; Most-Recent; Effective

Status: Effective

CLARVISTA MEDICAL PROTOCOL CVM-00001 REV.03

If the study lens is explanted, one postoperative visit should be completed to record best-corrected distance visual acuity (BCDVA) before the subject is discontinued. The sponsor will provide a commercially available IOL to replace the explanted study lens.

Subjects who withdraw from the study will be asked to complete procedures outlined in the 1 Month Visit (if withdrawn prior to that visit). Subjects who are terminated due to an AE will be followed, if possible, at least until resolution or stabilization of the AE. Subject withdrawals will be documented clearly on the source document and applicable CRF.

Prior to discontinuing a subject, every effort should be made to contact the subject, schedule a final study visit, and obtain as much follow-up data as possible. Adverse events will be followed as described in Section 6.3.4. Discontinued subjects should be followed outside of the study protocol according to the Investigator's normal postoperative standard of care.

A Study Exit CRF must be completed for all subjects who discontinue from the clinical investigation.

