The CVM-00001 study is designed as a prospective, multi-center, cohort study. Any pre-planned formal hypothesis tests for this feasibility study are not for the purposes of generating definitive conclusions to support regulatory approval.

The study was carried out at five investigational centers, in the Philippines (3 centers), Panama (1) and Mexico (1).

The study comprises patients with planned removal of cataracts (cortical, nuclear, subcapsular, or a combination) by manual phacoemulsification. The investigator will determine if the test lens is to be implanted in OD, OS, or OU based on target refraction and the best interests of the subject.

All patients will have visits scheduled for 1 Day, 1 Week, and 1 Month following primary cataract extraction. During follow up the Investigator and Subject will decide if an optic exchange in the study eye is in the best interests of the subject based on refractive outcome and target. Subjects with satisfactory outcomes, or those opting not to pursue an optic exchange, will be entered into Cohort 1.

Subjects who opt for an HMIOL optic exchange in their primary eye will be entered into Cohort 2. Optic exchange patients will have visits scheduled for 1 Day, 1 Week, and 1 Month following the optic exchange procedure. These subjects may be followed up beyond 1 month as deemed necessary by the surgeon.

Several cohorts of subjects are specified to help characterize the clinical significance of the study outcomes in eyes with and without optic exchange. These cohorts are defined as follows:

All HMIOL Eyes Cohort: Defined as all study eyes implanted with the study device.

Cohort 1: Defined as the subset of study eyes implanted with the study device without a subsequent optic exchange procedure.

Cohort 2: Defined as the subset of study eyes implanted with the study device with a subsequent optic exchange procedure. Analysis of follow-up visits for this cohort will cover two separate time periods:

- Pre-Optic Exchange, comprising visits following primary cataract extraction, prior to the optic exchange visit (through 1 month).
- Post-Optic Exchange, comprising visits following optic exchange. The baseline for the post-optic
 exchange visits is the last pre-optic exchange visit (1-month).

Separate analyses are planned for each cohort.

Rev.02, 1 March 2018 Confidential Page 3 of 8

Document: TDOC-0056125 **Version:** 1.0; CURRENT; Most-Recent; Effective

Status: Effective

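### Section 4.5 discontinues the whole subject when one study lens is explanted or a complication prevents implantation, so a subject with the lens in both eyes also loses follow-up of the sound eye

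*Protocol*

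**What the plan says.** Protocol section 4.5 is mandatory and worded per subject: "A subject MUST be discontinued prior to the final study visit for any of the following reasons". Two of its four listed reasons matter here: "Explantation of the HMIOL System" and "Surgical complication(s) unrelated to the investigational device preventing the implantation of the HMIOL". Neither mentions an eye.

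After an explant, one postoperative visit is to record best-corrected distance acuity (BCDVA). Sites are also to try to arrange a final visit and collect what they can. Then "Discontinued subjects should be followed outside of the study protocol according to the" investigator's usual postoperative practice.

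On who receives the lens, SAP section 4 (Design and Objectives) says: "The investigator will determine if the test lens is to be implanted in OD, OS, or OU". The protocol synopsis agrees, so one subject can have two HMIOL eyes.

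The SAP works by eye. Section 4 defines the All HMIOL Eyes Cohort and Cohorts 1 and 2 as sets of study eyes, section 7 defines the Safety and Per-Protocol populations as eyes, and section 5.3 bases accountability on eyes. Section 5.3 gives four reasons why an eye may be unavailable, one of which is that the subject was discontinued. Missing results are not imputed (protocol 8.3, SAP 5.1).

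**The concern.** The stopping rule and the analysis use different units. A site that follows section 4.5 must discontinue an OU subject when one lens comes out, although the other eye still carries the device and belongs to the SAP's populations. No section of either document discontinues a single eye or keeps the remaining HMIOL eye on schedule.

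Two things are at stake:

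- **The loss is not random.** The sound eye leaves because its fellow had a device or surgical failure. The two eyes share the patient and the device, and may share the surgeon, so these eyes are of particular interest for safety.
- **The reported reason hides it.** Under SAP 5.3 the explanted eye and its still-implanted fellow both appear as belonging to a discontinued subject. A reader of that table cannot tell them apart.

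**Working it through.** **Step 1. Which triggers reach a subject who already has one HMIOL eye?**

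| Text | Reaches the sound fellow eye? |
|---|---|
| 4.5, explantation | Yes. An explant in either eye meets it. This is the clearest case. |
| 4.5, complication preventing implantation | Yes, when second-eye surgery fails after the first eye has its lens. It is not limited to Day 0. |
| 4.5, not implanted with an HMIOL at Day 0 | Doubtful. A subject with one HMIOL has been implanted with one. |
| 3.3.2, no HMIOL implanted because of an intra-operative complication | Doubtful, for the same reason. |

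The point rests on the first two rows.

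**Step 2. What is still collected for the sound eye?** One BCDVA visit is required after an explant (4.5), and a final visit is sought (4.5). Ongoing SAEs and ADEs are followed until they resolve or stabilise (6.3.4). Scheduled visits end. AE reporting runs only to the last study visit (6.0), so a new event after exit falls outside required collection. A final visit before Day 30 also falls outside the 1 Month window of Days 30 to 60.

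**Step 3. How many eyes?** The plan has no figure to reproduce. The only documented input is the maximum of 200 subjects (synopsis and 3.1). Three inputs are assumed:

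- OU share b: 10% or 40%.
- Per-eye chance q of explant before the final visit: 1% or 5%.
- Independence between eyes.

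OU subjects = 200b. HMIOL eyes = 200(1 + b). The chance that exactly one of two eyes is explanted is 2q(1 − q), which is 0.0198 at q = 1% and 0.095 at q = 5%. Sound eyes discontinued = 200b × 2q(1 − q).

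| b | q | HMIOL eyes | Sound eyes discontinued | Share of HMIOL eyes |
|---|---|---|---|---|
| 10% | 1% | 220 | 20 × 0.0198 = 0.396 | 0.18% |
| 10% | 5% | 220 | 20 × 0.095 = 1.9 | 0.86% |
| 40% | 1% | 280 | 80 × 0.0198 = 1.584 | 0.57% |
| 40% | 5% | 280 | 80 × 0.095 = 7.6 | 2.7% |

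These are ceilings for the explant route. They treat every sound eye as implanted and still awaiting its 1 Month visit when its fellow is explanted. If only a fraction f is in that position, multiply by f. At f = 0.5, for illustration, the range is 0.2 to 3.8 eyes. Positive correlation between eyes would lower the counts, because more explants would be bilateral. Failed second-eye implantations are not counted, because no rate is given; each could add at most one sound eye. With b = 0 every figure is zero, and an eye-level rule also gives zero.

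**Step 4. Does the accountability percentage show the loss?** SAP 5.3 divides eyes available by eyes enrolled minus discontinued minus active. Take 100 OU subjects (200 eyes), 5 one-eye explants, and all other eyes seen:

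- Subject-level rule: 190 / (200 − 10) = 100%.
- Eye-level rule: 195 / (200 − 5) = 100%.

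The percentage is the same either way. Only the count of discontinued eyes differs, 10 against 5.

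**The case against.** The strongest reply is that the protocol often reads as if each subject had one study eye. Section 3.2.4 has "Presence of YAG Capsulotomy in the primary (HMIOL) eye", section 3.3.6 also refers to a primary study eye, and section 4.9.2 lists a fellow-eye lens as a concomitant procedure. On that reading section 4.5 is simply an unadapted subject-level clause. This explains the wording but does not remove the conflict, since the synopsis and SAP section 4 both allow OU implantation.

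The reply also says that the events are few, the study is descriptive, and a final visit is sought. All of that stands and limits the severity.

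A reader might infer more than the documents support:

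- **That section 3.3.2 states the same rule.** Its words are "In the event the subject is not implanted with an HMIOL device due to an intra-operative complication, the subject will be discontinued". A subject with one HMIOL in place does not clearly meet that condition.
- **That SAP section 10 requires every eye to reach 1 Month.** It only sets when the interim safety summary is run. Final outcomes are evaluated once subjects complete or exit.
- **That section 4.5 causes the unchanged accountability percentage.** It does not: subtracting discontinued eyes has that effect under either rule.
- **That explants cannot be traced.** They can: section 6.3.1 requires every explant to be reported within 24 hours. What is missing is the split in the accountability table.
- **That second eyes have no unscheduled-visit data.** Section 3.3.6 says "Only data relevant to the primary study eye (if applicable) will be captured on the Unscheduled Visit CRFs". This depends on whether primary means one eye or every HMIOL eye, and the same section still records AEs and concomitant medications.

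**Conclusion.** The point holds as a minor one. Read as written, section 4.5 takes a still-implanted HMIOL eye out of scheduled follow-up and new-AE collection because the other eye was explanted or its implantation failed. The evidence is clearest for explants; for failed implantation it rests on the complication bullet alone.

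Through explants, the ceiling is about 0.4 to 7.6 eyes, or 0.2% to 2.7% of HMIOL eyes. This is not an expected count. It rests on the assumed OU shares and explant chances and on independence between eyes, and it gives no credit for a 1 Month visit already done or for the final visit. Subjects with one HMIOL eye are unaffected.

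The study tests no hypothesis, so no formal conclusion is at risk. The reason to act is that the loss is informative about safety and easy to prevent.

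**What to change.** - **Protocol 4.5.** Apply the explantation and complication bullets to the affected eye. End that eye's follow-up after its BCDVA visit where it was explanted. Keep any remaining HMIOL eye on its scheduled visits, and discontinue the subject only when no HMIOL eye remains.
- **SAP 5.3.** Replace the single discontinued-subject reason with two: eye explanted or not implanted, and subject left the study.

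The cost is a few words in two places, plus completion of visits already scheduled for the remaining eye. Nothing changes for subjects with one HMIOL eye. SAP section 4 describes the conduct of the study in the past tense. If follow-up has ended, the protocol change comes too late, but the SAP 5.3 split can still be made and would show whether any such eyes exist.

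Clarifying sections 3.1, 3.3.2 and 3.3.6 and the AE reporting window for OU subjects would be tidy, but it is optional and this point does not depend on it.
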